#### 13.6 Secondary Outcomes

- (1) For the proportion of participants with 3 or more mean weekly CSBMs, the Cochran-Mantel-Haenszel (CMH) test, stratified by center, was used to test a hierarchical comparison between two groups. Assessing timeframe: weeks 1-2, 11-12, 15-16, 19-20, 31-32.
- (2) For the proportion of participants with ≥1 increase of mean weekly CSBMs from baseline, the Cochran-Mantel-Haenszel (CMH) test, stratified by center, was used to test a hierarchical comparison between two groups. Assessing timeframe, weeks 1-2, 3-8, 11-12, 15-16, 19-20, 31-32.
- (3) For the change from baseline in mean weekly CSBMs, a repeated measures analysis of variance was used, setting group, time, and the interaction of group and time as the fixed effects; besides, the baseline CSBMs data and usage of rescue medicine were set as the covariate. Assessing timeframe: weeks 1-2, 3-8, 11-12, 15-16, 19-20, 31-32.
- (4) For the change from baseline in mean weekly SBMs, the same statistical analysis was conducted in accordance with the change from baseline in mean weekly CSBMs. Assessing timeframe: weeks 1-2, 3-8, 11-12, 15-16, 19-20, 31-32.
- (5) For the mean scores of straining, the Wilcoxon rank-sum test was used. Assessing timeframe: weeks 1-2, 3-8, 11-12, 15-16, 19-20, 31-32.
- (6) For the mean scores of stool consistency, the Wilcoxon rank-sum test was used. Assessing timeframe: weeks 1-2, 3-8.
- (7) For the time to the first CSBM (counting by days), the Wilcoxon rank-sum test was used.
- (8) For the change in mean scores of PAC-QOL between two groups, t test was used. Assessing time point: week 4 and week 8.
- (9) Rescue medicine usage: For the proportion of participants using rescue medicine (bisacodyl or glycerine enema), the Chi-square test was used. For the average dosage of bisacodyl or glycerine enema used per week, the Wilcoxon rank-sum test was used. Assessing timeframe: weeks 1-2, 3-8, 11-12, 15-16, 19-20, 31-32.
- (10) Post-hoc analyses: A weekly CSBM responder was defined as a patient who had ≥3 CSBMs for a given week and an increase from baseline of ≥1 CSBM for that same week. An overall CSBM responder was a patient who was a weekly CSBM responder for at least 6 of the 8 treatment weeks (75%). A sustained CSBM responder met the overall responder criteria, and also met the responder criteria for at least 3 of the last 4 treatment weeks. For proportion of the overall CSBM responder and sustained CSBM responder over weeks 1-8, Chi-square tests were used. For the weekly CSBMs and its changes from baseline of each week for data collection (week -2, week -1, weeks 1-8, weeks 11-12, weeks 15-16, weeks 19-20, weeks 31-32), a repeated measures analysis of variance was used, setting group, time, and the interaction of group and time as the fixed effects; besides, the baseline CSBMs data and usage of rescue medicine were set as the covariate.
- (11) For the acceptability of EA, the number and proportion of participants who accepted the treatment of electroacupuncture was describe.

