#### 10.3 Secondary Outcomes

- 1) The proportion of participants with 3 or more mean weekly CSBMs over weeks 1-2, 11-12, 15-16, 19-20, 31-32. The EA group was discontinued after 8 weeks of treatment, while the drug group continued to take prucalopride for 24 weeks in the absence of QT interval elongation or other severe cardiac adverse events (like myocardial infarction, severe arrhythmia, etc.). Assessing time frame: weeks 1-2, weeks 11-12, 15-16, 19-20, 31-32
- 2) The proportion of participants with  $\geq 1$  increase of mean weekly CSBMs from baseline over weeks 1-2, 3-8, 11-12, 15-16, 19-20, 31-32. Assessing time frame: baseline, weeks 1-2, weeks 3-8, weeks 11-12, 15-16, 19-20, 31-32.
- 3) The change from baseline in mean weekly CSBMs over weeks 1-2, 3-8, 11-12, 15-16, 19-20, 31-32. Assessing time frame: baseline, weeks 1-2, weeks 3-8, weeks 11-12, 15-16, 19-20, 31-32.
- 4) The change from baseline in mean weekly SBMs over weeks 1-2, 3-8, 11-12, 15-16, 19-20, 31-32. Assessing time: baseline, weeks 1-2, weeks 3-8, weeks 11-12, 15-16, 19-20, 31-32.
- 5) The change from baseline in the mean score of stool consistency of each SBM over weeks 1-2 and weeks 3-8. Assessing time: baseline, weeks 1-2 and weeks 3-8. Participants will self-report their stool consistency of each SBM according to the 7-type BSFS (scored by 1 to 7 respectively).

- Type 1: Separate hard lumps, like nuts (hard to pass)
- Type 2: Sausage-shaped, but lumpy
- Type 3: Like a sausage but with cracks on its surface
- Type 4: Like a sausage or snake, smooth and soft
- Type 5: Soft blobs with clear cut edges (passed easily)
- Type 6: Fluffy pieces with ragged edges, a mushy stool
- Type 7: Watery, no solid pieces. Entirely liquidz
- 6) The change from baseline in the mean score of straining of each SBM over weeks 1-2, weeks 3-8, weeks 11-12, 15-16, 19-20, 31-32. Assessing time: baseline, weeks 1-2, 3-8, 11-12, 15-16, 19-20, 31-32. Participants will self-report their straining degree of each SBM in the defecation diaries according to the following scale:
  - 0 = not difficult;
  - 1 = a little difficult, need some straining to defecate;
  - 2 = difficult, need straining to defecate;
  - 3 = very difficult, need hard straining to defecate.

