#### 13. Statistical Analysis

### 13.1 Objective and Hypothesis

#### Objective

Through comparing the efficacy of EA and prucalopride, we aim to evaluate if the effect of EA will be non-inferior to that of prucalopride. We also will evaluate if the therapeutic effect of EA could sustain for 3~6 months.

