### 13.3 General Principles of Statistical Analysis

The primary outcome was one-tailed test at significance levels of 0.025. All the other statistical analyses were two-tailed tests, at a significant level of 0.05, using SAS software, version 9.4 (SAS Institute Inc, Cary, North Carolina, USA). For measurement data, mean±standard deviations (M±SD), median, minimum, maximum, were presented. Differences between groups were compared using group t tests or nonparametric tests. Comparisons with the baseline used paired t tests or nonparametric tests. For counting data, cases and percentages were presented, and differences between groups were compared using Chi-squared tests, Fisher's exact probabilities or non-parameters tests. For abnormal distributed data, differences between groups were compared using nonparametric tests. Missing data for the primary outcome were imputed using the multiple imputation (MI) method under the missing at random assumption for the mITT population. The results for the PP set were used as the sensitivity analysis for the multiple imputation. For secondary outcomes, no imputation was used and observed data were used for analyzing.

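### The repeated-measures ANOVA for CSBM and SBM change spans two windows on EA and four after EA, but names no target contrast, covariance structure or centre term, and leaves the SBM baseline covariate unclear

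*Supplement*

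**What the plan says.** SAP 10.3 item 3 defines the outcome window by window: "The change from baseline in mean weekly CSBMs over weeks 1-2, 3-8, 11-12, 15-16, 19-20, 31-32". Item 4 does the same for SBMs.

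SAP 13.6(3) then analyses all six windows together: "a repeated measures analysis of variance was used, setting group, time, and the interaction of group and time as the fixed effects", and "the baseline CSBMs data and usage of rescue medicine were set as the covariate". Item (4) says of SBMs that "the same statistical analysis was conducted in accordance with the change from baseline in mean weekly CSBMs". Testing follows SAP 13.3: "All the other statistical analyses were two-tailed tests, at a significant level of 0.05". That section also uses observed data without imputation for secondary outcomes.

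The arms differ after week 8. SAP 10.3 says "The EA group was discontinued after 8 weeks of treatment, while the drug group continued to take prucalopride for 24 weeks", subject to a cardiac condition. Persistence is a separate aim in SAP 13.1: "We also will evaluate if the therapeutic effect of EA could sustain for 3~6 months".

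The SAP does not state the contrast to be reported, the covariance structure, a sphericity correction, or a centre term. Randomisation is stratified by centre (SAP 4), and the CMH tests in 13.6(1)-(2) respect that. Final protocol 7.3 does not fill the gap: it mentions only two-sample tests for continuous data.

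**The concern.** The six windows do not measure one thing. Weeks 1-2 and 3-8 compare EA being given with prucalopride being given. Weeks 11-12, 15-16, 19-20 and 31-32 compare EA withdrawn with prucalopride continuing. Weeks 3-8 is also a six-week mean, while the other five are two-week means and therefore noisier.

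A repeated-measures ANOVA offers a group term, an interaction and any number of window contrasts. With none named, the choice is left to the time of analysis, and the group term is the easiest to report. The default classical fit also assumes a common variance, and often complete data, neither of which suits these windows. At stake is whether the two main continuous efficacy outcomes yield a clear on-treatment estimate and a clear persistence estimate, each with a correct interval.

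**Working it through.** **Plan's own figure.** The SAP gives no number for this analysis. Its sample size, used below only as the arm size, reproduces: 2.49² × (0.3167×0.6833 + 0.309×0.691) / 0.1077² = 229.8, so 230 per group.

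**1. Weight of the group main effect.** With equal weight per window, main effect = (2 × on-EA difference + 4 × post-EA difference) / 6, so 2/6 = 33% is on EA and 4/6 = 67% is after it. Even weighted by diary weeks, only 8 of 16 weeks are on EA. Illustrations in CSBMs per week, EA minus prucalopride (assumed, not predicted):
- +0.5 on and −0.25 after: (1.0 − 1.0)/6 = 0
- +0.3 on and −0.6 after: (0.6 − 2.4)/6 = −0.3

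**2. Standard errors if one common variance is fitted.** The documents give no SDs. Assume between-person SD *b* of 1-2 and week-to-week SD *w* of 1-1.5 CSBMs, with independent weekly errors. Then:
- six-week mean: V6 = b² + w²/6
- two-week mean: V2 = b² + w²/2
- average over the six windows: Vbar = (5·V2 + V6)/6 = b² + 0.444w²
- fitted SE divided by true SE: √(Vbar/V6) for weeks 3-8, and √(Vbar/V2) for a two-week window

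| b | w | V6 | V2 | Vbar | Weeks 3-8 | Two-week |
|---|---|---|---|---|---|---|
| 2 | 1 | 4.167 | 4.5 | 4.444 | 1.03 | 0.99 |
| 1.5 | 1 | 2.417 | 2.75 | 2.694 | 1.06 | 0.99 |
| 1.5 | 1.5 | 2.625 | 3.375 | 3.25 | 1.11 | 0.98 |
| 1 | 1.5 | 1.375 | 2.125 | 2.0 | 1.21 | 0.97 |

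Put instead as the between-person share of single-week variance, a range of 0.2-0.8 gives 3-29% too large at weeks 3-8 and about 1-4% too small at two-week windows. Adjusting for a two-week baseline mean raises the weeks 3-8 figure to 21-35%.

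**3. The group main effect's own SE.** With complete data this effect is tested on each participant's mean over the windows. The ratio of common-variance SE to true SE is 1.000 throughout. A simulation (230 per arm, 4,000 runs, complete data, no baseline adjustment, nominal 0.05) gives these type I error rates:

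| Between-person share | Main effect | Weeks 3-8 | Two-week window |
|---|---|---|---|
| 0.3 | 0.043 | 0.015 | 0.054 |
| 0.5 | 0.050 | 0.028 | 0.057 |
| 0.7 | 0.047 | 0.040 | 0.050 |

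So the error falls on window-specific contrasts. It is conservative at weeks 3-8 and close to nominal elsewhere.

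**4. Complete-case fit.** If 20% lack at least one window (borrowing the sample-size dropout allowance as an assumption), the weeks 3-8 SE grows by 1/√0.8 = 1.12.

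**5. SBM covariate.** Let ρ be the correlation of baseline with follow-up SBMs, and r that of baseline SBMs with baseline CSBMs. Take equal variances, and assume baseline CSBMs relate to follow-up SBMs only through baseline SBMs. Residual variance of the change is 1 − ρ² with the SBM baseline as covariate and 2(1−ρ) − r²(1−ρ)² with the CSBM baseline. The share of precision lost is one minus their ratio:
- ρ = 0.5, r = 0.4: 1 − 0.75/0.96 = 22%
- ρ = 0.7, r = 0.6: 1 − 0.51/0.5676 = 10%
- ρ = 0.3, r = 0.2: 1 − 0.91/1.3804 = 34%

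**The case against.** A reader might infer that the plan's headline result is an average over all windows and that its standard error is wrong. The documents support neither claim. The interaction is in the model, so window-specific differences can be estimated from it. The outcomes are defined by window, and the group main effect is never named as the result. Follow-up windows belong in the analysis because persistence is an objective. Step 3 shows that, with complete data, the main effect's SE is right. How far dropout would change that was not computed.

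The other parts are conditional too. Describing fixed effects and using SAS 9.4 is compatible with a mixed model and an unstructured covariance. Using observed data does not prescribe complete cases. The 20% is a planning allowance, not a forecast of missing week-32 diaries. Most analysts would take the same analysis for SBMs to mean SBMs with their own baseline.

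All of that stands, and it limits the point to what happens under particular readings. It does not remove the point, because the SAP commits to none of the favourable readings. The method it names has a classical form in which the common-variance and complete-case problems do arise. The absence of centre from the stated terms does not depend on any reading.

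**Conclusion.** The concern holds as a conditional weakness in the specification of two secondary analyses.

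- **Contrast:** if the group main effect is reported, two-thirds of its weight is post-EA and it answers neither question. This is arithmetic and needs no assumption beyond equal window weights.
- **Standard errors:** if a common variance is fitted, the weeks 3-8 SE is roughly 3-21% too large under the assumed SDs without baseline adjustment, and two-week SEs are about 1-4% too small. The error is conservative for weeks 3-8.
- **Missing windows:** a complete-case fit would cost about 12% in SE at an assumed 20% loss.
- **SBM baseline:** read literally, item (4) loses about 10-34% of precision, depending on assumed correlations.
- **Centre:** the stratification factor is left out. The documents give no figure from which to size this.

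The primary CMH analysis and its conclusion are untouched.

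**What to change.** Replace the model in SAP 13.6(3)-(4) with a mixed model for repeated measures:

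- **Terms:** group, window, group-by-window, the outcome's own baseline (CSBMs for item 3, SBMs for item 4), baseline-by-window, and centre.
- **Covariance:** unstructured, with heterogeneous Toeplitz as the named fallback if the fit does not converge.
- **Data:** every observed window, so a missing late diary does not remove a participant from weeks 3-8.
- **Reporting:** the six window-specific group differences with 95% CIs. Weeks 3-8 is the on-treatment result, weeks 1-2 the early result, and the four later windows the persistence results. The pooled group main effect is not used as the result.
- **Rescue medicine:** state whether this covariate is kept or removed, and why. It is measured after randomisation and may itself respond to treatment, so either choice changes what is estimated.

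The post-hoc weekly model in 13.6(10) uses the same wording and should be brought into line.

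The cost is a few lines of SAP text and standard SAS code, with no new data. An unstructured 6×6 covariance has 6×7/2 = 21 parameters and 14 centres use 13 degrees of freedom, both modest against 230 per arm. The rescue-medicine decision is the one item that needs its own argument.

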### 2.4.5.2 Exclusion Criteria:

- 1) Irritable bowel syndrome, organic constipation or secondary constipation caused by endocrine, metabolic, nervous, postoperative diseases, or drugs;
- 2) More than one mushy or watery stool during baseline while not taking laxatives (Bristol stool type 6 or 7);
- 3) A history of pelvic floor dysfunction;
- 4) Taking medicine that can influence the intestinal function or induce constipation (However, during the trial, participants are allowed to take drugs for other diseases which may affect the evaluation of the efficacy, the usage of the drugs should be recorded in detail)
- 5) Severe haemorrhoid or anal fissure;
- 6) Participants with severe cardiovascular, hepatic or renal diseases, cognitive impairment, abdominal aortic aneurysm or hepatosplenomegaly, aphasia, mental disorders, or illness that will influence the examination or treatment;
- 7) Women in the gestation or lactation period;
- 8) Participants with blood coagulation disorders or taking anticoagulants regularly, such as Warfarin and Heparin;
- 9) Participants with a cardiac pacemaker.

\*Notes for the screening and baseline evaluation (run-in) period: ① Medical history and physical examination were needed. Secondary constipation should be noticed if any symptom or sign of medical history suggests that constipation may be secondary; ② Colonoscopy is recommended for participants ≥50 years; ③ Colonoscopy may also be needed if any of the following alarming signs or/and symptoms occurs in any age: gastrointestinal bleeding, anemia, progressive weight loss, abdominal mass, significant abdominal pain, history of colon polyps especially in participants with family history of colorectal cancer; ④ The stool routine test and occult blood test must be done in each prospective case; ⑤ Baseline assessment (run-in) for 2 weeks: participants should discontinue laxatives or other medications and measures for constipation (except for rescue medicine) and maintain the usual diet and lifestyle. During baseline assessment (run-in) period, participant's gender, age, course of constipation, previous treatment for constipation, bowel movements, spontaneous defecation or not, complete evacuation or not, stool consistency, degree of straining, rescue medicine usage will be recorded

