#### 7.4 Rescue Medicine

Bisacodyl (5–10 mg) and glycerin enema (110 ml) can be used for participants who fail to have a bowel movement for 3 or more consecutive days. Furthermore, the date, specific time, dose of bisacodyl or glycerin enema using should be recorded in the defecation diary and case report form (CRF).

Other drugs or measurements for constipation are not allowed; However, details of the date, specific time, dose should also be recorded in the defecation diary and CRF if used. Rescue medicine is available during the whole study period (baseline assessment [run-in], treatment, and follow-up); nevertheless, it is not allowed 48 hours before and after the first treatment, no matter EA or prucalopride, in order to evaluate the time to the first spontaneous defecation. Rescue medicine will be distributed to the participants beforehand every 2 weeks in the treatment period, and every 4 weeks in the follow-up period.

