#### 10. Subject Evaluations and Outcomes

#### 10.1 Baseline Evaluations

Outcomes contain the complete spontaneous bowel movements (CSBMs), spontaneous bowel movements (SBMs), stool consistency (according to Bristol Stool Scale), straining during the defecation, rescue medicine used, and the form of Chinese-version Patient Assessment of Constipation Quality of Life (PAC-QOL). Participants will record their bowel movements, constipation-related symptoms, medicine used for constipation every day through week -2, week -1, weeks 1-8, weeks 11-12, weeks 15-16, weeks 19-20, and weeks 31-32. In both groups, participants without bowel movements (BMs) for 3 or more consecutive days were allowed to use bisacodyl (5-10mg a day before bedtime, Boehringer Ingelheim) or 110 ml glycerol enema as rescue medicine with documentation (time, dosage, and frequency of use) in the stool diary.

The SBMs are the bowel movements that occur in the absence of rescue medicine, or other assistant methods (laxatives, enemas, suppositories usage, or digging out by fingers) within the preceding 24 hours, which include the CSBMs. When participants used rescue medicine, or other measures for constipation, the defecation within 24 hours was considered a non-spontaneous bowel movement, whereas defecation exceeding 24 hours was deemed an SBM. CSBMs were the SBMs with the sensation of complete evacuation.

Outcome record time point: Baseline (the last day of week -2 and week -1), week 2, week 4, week 6, week 8, week 12, week 16, week 20, and week 32 (Figure 1).

[figure not shown]
Outcome assessing time frame: baseline period (weeks -2 to week -1), the latter 6-week treatment (weeks 3-8), the first 2-week treatment (weeks 1-2), and the follow-up periods (weeks 11-12, weeks 15-16, weeks 19-20, weeks 31-32).

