- 7) Time to the first CSBMs, which was the time from the first treatment to the first CSBMs counting by days. Rescue medicines are not allowed to be used during 48 hours before and after the first treatment. If the first CSBM had not occurred yet, and rescue medicines were used in the condition of no BM in a succession of three or more days, the BM occurs within 24 hours after the use of rescue medicine will not be regarded as CSBM, and the days-counting will continue till the occur of the first CSBM.
- 8) The change from baseline of the score of PAC-QOL at week 4 and week 8. PAC-QOL is a self-report questionnaire to evaluate the quality of life in participants with constipation, which was distributed by Mapi Research Trust in France. This questionnaire contains 28 items including 4 basic parts of physical discomfort, worries and concerns, psychosocial discomfort, and satisfaction. We use the Chinese version in our trial16. Assessing point: baseline, week 4 and week 8.
- 9) The proportion of participants using rescue medicine (bisacodyl or glycerol enema) and the mean weekly dosage of rescue medicine used ((bisacodyl or glycerol enema) over weeks 1-2, 3-8, 11-12, 15-16, 19-20, 31-32. Assessing time frame: baseline, weeks 1-2, 3-8, 11-12, 15-16, 19-20, 31-32.

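### The models for change in CSBMs and SBMs adjust for rescue use without limiting it to the run-in, so the group effect may not be the effect of randomised treatment

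*Supplement*

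**What the plan says.** SAP 13.6 item (3) fits group, time and group-by-time as fixed effects to the change in mean weekly CSBMs over six post-randomisation windows, and adds that "the baseline CSBMs data and usage of rescue medicine were set as the covariate". Item (4) carries the CSBM model over to SBMs, in a sentence that begins: "For the change from baseline in mean weekly SBMs, the same statistical analysis was conducted in accordance with the change from baseline in mean weekly". Item (10), labelled post-hoc, repeats the covariate sentence for CSBMs week by week.

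Rescue use appears elsewhere in three other roles.

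- **Response to lack of effect.** Under SAP 7.4, bisacodyl or a glycerin enema "can be used for participants who fail to have a bowel movement for 3 or more consecutive days". The same section states: "Rescue medicine is available during the whole study period (baseline assessment [run-in], treatment, and follow-up").
- **Outcome.** SAP 10.3 item 9 lists "The proportion of participants using rescue medicine (bisacodyl or glycerol enema) and the mean weekly dosage of rescue medicine used" as a secondary outcome. SAP 13.6 item (9) compares it between arms over weeks 1-2, 3-8, 11-12, 15-16, 19-20 and 31-32: "For the proportion of participants using rescue medicine (bisacodyl or glycerine enema), the Chi-square test was used", with a Wilcoxon test for weekly dosage.
- **Part of the endpoint definition.** Under SAP 10.1, after rescue, "the defecation within 24 hours was considered a non-spontaneous bowel movement".

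Rescue use is also collected before randomisation. The run-in notes under section 2.4.5.2 of the final protocol end with "stool consistency, degree of straining, rescue medicine usage will be recorded". The SAP does not name this run-in variable as the covariate. Section 7.3 of the final protocol gives only generic two-sample tests and does not mention the covariate.

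**The concern.** A covariate measured after randomisation and affected by treatment changes what the group term estimates. Patients who respond have fewer runs of days without a bowel movement and so qualify for rescue less often. Comparing arms at equal rescue use does two things. It removes any part of the treatment effect that passes through rescue, including movements no longer lost to the 24-hour rule. It also compares unlike patients, because at the same level of rescue use the arm with the better response will contain the more severely constipated patients.

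At stake are the between-arm estimates of mean CSBM and SBM change at every window. The follow-up windows bear on the stated question of whether the EA effect lasts 3 to 6 months. By SAP 10.3 item 1, EA has stopped by then while prucalopride continues for up to 24 more weeks, so equal rescue use cannot be presumed. SAP 13.6 plans no version of these models without the covariate.

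**Working it through.** **1. Which rescue use is meant?** In the covariate sentence, *baseline* stands directly before the CSBM data, and rescue use follows with no window. The rescue variables analysed in item (9) are all post-randomisation. On-study use is therefore the natural reading. The wording does not exclude run-in use.

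**2. Is there a figure to reproduce?** No. The documents give no effect size, standard deviation or rescue rate for these models. What follows is an illustration with assumed coefficients, at a single time point.

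**3. Set-up.** Let A be the arm, U an unmeasured severity with variance 1, B the baseline value, R on-study rescue use and Y the outcome. Each noise term e is independent with variance 1.

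- B = 0.5U + 0.87e
- R = 1 − aA + gU + e
- Y = 1 + τA − bU + cR + e

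The total effect of assignment is τ − ca. Holding B and R fixed, the expected value of U shifts with A by ga / (1 + 0.5²/0.87² + g²). With g = 0.5 this is 0.5a / (1 + 0.3303 + 0.25) = 0.3164a. The adjusted group effect is therefore τ − 0.3164ab, which for b = 0.5 is τ − 0.158a.

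**4. Results** (CSBMs per week; simulation with 400,000 participants per row):

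| τ | a | c | b | Total effect | Adjusted for on-study rescue, formula | Same, simulated | Baseline only, simulated | Baseline + run-in rescue, simulated |
|---|---|---|---|---|---|---|---|---|
| 0.5 | 0 | −0.3 | 0.5 | 0.50 | 0.50 | 0.50 | 0.50 | 0.50 |
| 0.5 | 0.3 | −0.3 | 0.5 | 0.59 | 0.45 | 0.46 | 0.60 | 0.60 |
| 0.5 | 0.5 | −0.3 | 0.5 | 0.65 | 0.42 | 0.42 | 0.65 | 0.65 |
| 0 | 0.3 | −0.3 | 0.5 | 0.09 | −0.05 | −0.04 | 0.09 | 0.09 |
| 0 | −0.3 | −0.3 | 0.5 | −0.09 | 0.05 | 0.05 | −0.09 | −0.09 |
| 0 | 0.3 | 0 | 0.5 | 0.00 | −0.05 | −0.05 | 0.00 | 0.00 |
| 0 | 0.3 | 0 | 0 | 0.00 | 0.00 | 0.00 | 0.00 | 0.00 |

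For example, in row 2 the total effect is 0.5 + 0.3 × 0.3 = 0.59 and the adjusted effect is 0.5 − 0.158 × 0.3 = 0.45. With c = −0.3 and b = 0.5, adjusted minus total is −(0.3 + 0.158)a = −0.458a. That is −0.14 at a = 0.3 and −0.23 at a = 0.5.

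**5. Reading the table.** There is no bias if the arms have equal rescue use (row 1), or if rescue neither affects the outcome nor shares a cause with it (row 7). Otherwise, in this model, the estimate moves against the arm that uses less rescue. Run-in rescue does no harm in any row.

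**6. A pure-null illustration.** Take 280 per arm with outcome 1.2 + 0.8u + N(0, 1), rescue 0.8 + a·arm − 0.5u + N(0, 0.7) and baseline 0.4u + N(0, 0.8), where the second entry is the standard deviation. Here u is a latent factor with variance 1 and there is no effect on CSBMs. The false effect is 0.8 × (0.5/0.49) / (1 + 0.16/0.64 + 0.25/0.49) × a = 0.464a. This gives −0.09 at a = −0.2 and −0.19 at a = −0.4. In 2,000 replicates the two-sided 5% test rejected in about 16% and 45%, against 4-5% without the covariate.

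**The case against.** **Run-in rescue may have been meant.** *Baseline* could govern both nouns. Rescue use is listed under the Baseline Evaluations heading, is recorded in the run-in, and has baseline in the time frame of outcome 9. On that reading there is no bias and only the wording needs repair. This stands as a possibility. It does not rescue the sentence, because an analyst following it may take the other reading.

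**Bias requires a difference in rescue use.** This stands. The documents give neither the difference nor the coefficients, so size and direction are unknown.

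**The pure-null scenario is strained.** A reader might infer from step 6 that the test would give false positives 16% or 45% of the time. The documents do not support that. Rescue is triggered by days without a bowel movement, so a treatment that lowers rescue use would ordinarily do so by increasing bowel movements. The scenario is hardest to defend for SBMs. Distortion or attenuation of a real difference is the likelier result. The illustrations also use a single time point rather than the planned repeated-measures model.

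**Rescue has to be handled somehow.** The 24-hour rule reclassifies movements soon after rescue, but an enema may affect later days too. The rule therefore does not prove that nothing more is needed. Conditioning on on-study rescue is still not a remedy that leaves the randomised comparison intact.

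**The main conclusions do not rest on these models.** This stands. Another tempting inference is that the non-inferiority result is compromised. It is not: SAP 13.5 uses a CMH test stratified by centre with no rescue covariate. Responder items (1) and (2) do the same, and item (2) covers CSBM increase at the same six windows. SBM change has no such companion.

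**Conclusion.** The covariate is wrong as written and should be fixed; the point is limited to two secondary models and one post-hoc model. As the text naturally reads, items (3), (4) and (10) condition on a consequence of treatment that the SAP also analyses as an outcome. If the arms differ in rescue use, the group term does not estimate the total effect of assignment.

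This rests on two conditions: that on-study rescue use is meant, and that the arms differ in it. Under the assumed coefficients, the shift is 0.14 to 0.23 CSBMs per week for a difference in rescue of 0.3 to 0.5 uses per week, on true effects of 0.59 and 0.65. These figures show that the mechanism can matter. They are not an estimate for this trial, and the documents settle neither size nor direction.

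**What to change.** In SAP 13.6 items (3), (4) and (10), either delete rescue use from the covariates or define it explicitly as rescue use during the 2-week run-in. Either choice recovers the total effect in every scenario tabulated above. Keep the comparison of on-study rescue use in item (9). If a model adjusted for on-study rescue is still wanted, report it as a labelled supplementary analysis and state that it does not estimate the total effect of assignment. In the same edit, item (4) should say whether its baseline covariate is SBMs or CSBMs.

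The cost is one phrase and one model term. No new data are needed, since run-in rescue use is already recorded, and the sample size and primary analysis do not change.
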